10. DATA REPORTING

10.1 Data Collection and Submission

Data and/or completed Case Report Forms (CRFs) must be transmitted by fax or email to the Coordinating Center. Case report forms will be provided to the participating sites by the Coordinating Center.

The schedule for completion and submission of Case Report Forms to Johns Hopkins is as follows:

Form	Submission Timeline
Eligibility Checklist	Complete prior to registration
On-Study Form	Within 14 days of registration
Baseline Assessment Form	Within 14 days of registration
Treatment Form	Within 10 days of treatment completion
Adverse Event Report Form	Within 14 days of visit date
Response Assessment Form	Within 14 days of visit date
Off Treatment/Off Study Form	Within 14 days of completing treatment or being taken off study for any reason
Follow-up/Survival Form	Within 14 days of the protocol defined follow up visit date

The composite volumetric radiation therapy treatment plan will be submitted in a DICOM format to the Radiation Oncology PI (as feasible) in a manner determined appropriate for each participating institution. This information will include:

- DICOM RT dataset (structures, targets, dose, CT simulation study)
- Copy of the total dose records (treatment chart)

11. DATA SAFETY MONITORING

11.1 Monitoring Plan

This is a Level I study under the SKCCC Data Safety Monitoring Plan. Data Monitoring of this protocol will occur on a regular basis with the frequency dependent on the rate of subject accrual and the progress of the study. The protocol will be monitored internally

at SKCCC by [name] and externally by the SKCCC CRO in accordance with SKCCC guidelines. Trial monitoring and reporting will be done through the Safety Monitoring Committee at SKCCC.

Authorized representatives of the Coordinating Center may visit participating sites to perform audits or inspections, including source data verification. The purpose of these audits or inspections is to systematically and independently examine all trial related activities and documents to determine whether these activities were conducted and data were recorded, analyzed, and accurately reported according to the protocol, Good Clinical Practice (GCP), and any applicable regulatory requirements.

11.2 Stopping Rules

The study will enroll 20 patients and toxicity will be monitored continuously throughout. Any Grade 5 toxicity that is possibly related to radiation will suspend accrual until the study chair reviews the case. The criteria for severe adverse events to be considered clinically significant toxicities are presented in Section 7.1. We established a safety monitoring rule that will recommend stopping the study if there appears to be high probability that the adverse event (AE) rate is convincingly above 30%. Specifically, if the posterior probability of the AE rate exceeding 30% is 65% or greater, we will consider stopping the study for safety consultation. The prior distribution for the risk of AE is beta (0.5, 3.5), representing our prior guess at the AE rate is 12.5% on average and there is 90% certainty that it is between 0.05% and 45%. The stopping rules and corresponding operating characteristics based on 5000 simulations are shown in the tables below.

Suspend enrollment if	3 AEs	4 AEs	5 AEs	6 AEs	7 AEs	8 AEs
Out of N	3-5	6-8	9-11	12-14	15-17	18-20

True risk of AE	Probability declare treatment unsafe	Average sample size
0.20	13.7%	18.2
0.25	25.6%	16.8
0.30	41.2%	15.0
0.35	57.6%	13.2
0.40	73.7%	10.9
0.45	84.7%	9.3
0.50	92.2%	7.6

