5.6.2 At 3, 6, 9, 12, 18, 24, 30, and 36 months Post-SBRT

5.7 Duration of Follow-Up

It is anticipated the patients that remain on-study will be followed for 3 years.

Patients will remain enrolled on this protocol until there is evidence that their disease has progressed either locally or distally, at which case they will be removed from the protocol and be followed for survival only. Patients removed from study for unacceptable adverse events will be followed per protocol until resolution or stabilization of the adverse event and then followed for survival only.

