Toxicities commonly associated with such treatment will depend on the location of the treated metastasis. These toxicities can include skin erythema and desquamation, pain, neuropathy, dysphagia, nausea, vomiting, anorexia, and weight loss. Some of these symptoms can also be due to tumor progression. One significant toxicity is radiation pneumonitis, which can be manifested as fever, increased exertional dyspnea, pleuritic chest pain, and peritumoral infiltrate on chest imaging. It generally occurs between 1 to 3 months of completion of radiotherapy. The risk of grade 2-4 radiation pneumonitis is approximately 10-15% in patients treated with standard fractionated large field radiotherapy and higher in patients treated with combined chemoradiotherapy. It is highly dependent on the volume of the lung treated to high dose and the mean lung dose. At this point, the incidence of RT pneumonitis from stereotactic radiosurgery for small pulmonary tumors is unknown. However, if the treated tumor volume is kept \leq 65 cc, the risk should be $< 10-15\%$ with the proposed dose level. Also, given that this protocol focuses on SBRT to bone and spine, rather than lung, the risk of pneumonitis is expected to be low. Fracture is also a potential risk of radiotherapy to bone and spine, although doses in this study will be lower than the radiosurgery doses thought to put patients at high risk for fracture as reported in the literature (29).

Growth delay or arrest is a potential late effect of radiotherapy to bone for children who have not completed puberty. For this reason, patients in this protocol are limited

to those who have surgically unresectable disease or to those patients whose families refuse surgery. Given the data that demonstrates the improvement in clinical outcomes associated with aggressive local therapy in properly selected metastatic patients, the potential benefit of delivering a therapeutic dose of radiation likely outweighs the risks. The alternative treatment in this scenario is the delivery of subtherapeutic doses of radiation with palliative rather than curative intent.

Clinical and radiographic assessments will be performed as indicated to identify all adverse effects, ascertain their etiology, and provide the most appropriate palliative measures. Complications other than radiation pneumonitis, if any, will be graded according to the CTCAE version 4.0

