13.2 Sample Size/Accrual Rate

The primary endpoint of this trial is to estimate the local control of SBRT at 6 months. We anticipate that the local control rate will be roughly 90% as opposed to a 70% historical response with conventional moderate dose radiation. With 20 subjects participated, we will be able to estimate the local control rate to within 20% (i.e., maximum width of the 90% confidence interval reached is when the observed rate is 50%). If we observe a 6-month local control rate of 90%, we will be 90% certain that the true rate is greater than 70%. The associated exact 90% confidence interval will be (0.72, 0.98).

Using a Simon optimal two-stage design with a type I error of 10% and a type II error of 20%, the first stage would consist of 6 patients. A responder is considered to have local disease control at 6 months. If 4 or fewer patients respond, the study would terminate after the first stage. Otherwise, accrual would continue to a total of 20 patients. If 17 or more patients respond at the end of the second stage, the regimen with SBRT is considered promising (i.e., local control at 6 months is greater than 70%). This design has a 58% chance of early stopping when the true probability of response is 70% (the null hypothesis) and 11% chance of early stopping when the true probability of response is 90%.

The goal of enrollment is 20 patients. Based on the current institutional referral base, we expect that 12 patients will be eligible each year. Of these patients, we expect that two thirds will enroll on protocol. With this projection, we plan to complete accrual to the study in 3 years.

The proportion of patients with local control at six months will be reported with an exact binomial 90% confidence interval.

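### The toxicity rule's operating characteristics in 11.2 assume each patient's AE status is known before the next patient enters; with delayed toxicity the rule suspends later than printed, by an amount that depends on an onset time the plan does not give.

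*Combined protocol and SAP*

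**What the plan says.** Section 11.2: "The study will enroll 20 patients and toxicity will be monitored continuously throughout". The rule is Bayesian, with a Beta(0.5, 3.5) prior: "if the posterior probability of the AE rate exceeding 30% is 65% or greater, we will consider stopping the study for safety consultation". The printed boundary is 3 AEs out of 3-5, 4 of 6-8, 5 of 9-11, 6 of 12-14, 7 of 15-17 and 8 of 18-20. Its performance is given as follows: "The stopping rules and corresponding operating characteristics based on 5000 simulations are shown in the tables below". No accrual rate, onset time or reporting lag is stated for those simulations.

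Other sections bear on what N means:
- Section 7.1 counts Grade 3-5 non-hematologic toxicity as clinically significant and sets no observation window.
- Sections 9.1.1 and 13.4.1 make every patient evaluable for toxicity from the first SBRT treatment.
- Section 8 schedules toxicity assessment out to 36 months, and section 5.7 says "It is anticipated the patients that remain on-study will be followed for 3 years".
- Section 13.2 projects accrual: "we expect that 12 patients will be eligible each year. Of these patients, we expect that two thirds will enroll on protocol".
- Section 7.1 places pneumonitis 1 to 3 months after radiotherapy but expects its risk to be low here. It also says "Fracture is also a potential risk of radiotherapy to bone and spine", without a time, and names growth delay or arrest as a late effect.

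**The concern.** A count of AEs divided by patients treated estimates the AE rate only when those patients have had time to show an AE. If a patient joins N on the first day of treatment and toxicity appears months later, recent patients count as AE-free by default and pull the observed rate down. Looking at the data continuously does not change this, because it does not make outcomes available sooner.

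This boundary is the plan's only quantitative safety rule, for a regimen whose complication rate section 7.1 says is hard to predict. If its printed properties hold only for immediate toxicity, more patients may be treated at an unsafe rate than the committee was told to expect. A report that the boundary was not crossed could also mean only that toxicity had not yet been observed. And because N is not tied to follow-up, two monitors could compute different values from the same data.

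**Working it through.** **1. Boundary.** Suspend at the smallest x with 1 - BetaCDF(0.30; 0.5 + x, 3.5 + n - x) >= 0.65. For 3 of 5 this is 1 - BetaCDF(0.30; 3.5, 5.5) = 0.692 (suspend). For 3 of 6 it is 1 - BetaCDF(0.30; 3.5, 6.5) = 0.604 (continue). The printed cells reproduce exactly for n = 3 to 20. The same formula also suspends at 2 of 2, where 1 - BetaCDF(0.30; 2.5, 3.5) = 0.703; the table does not print that cell.

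**2. Printed operating characteristics.** Exact patient-by-patient binomial recursion to n = 20, each outcome known before the next entry, 2 of 2 included:

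| True AE rate | Printed: P(unsafe) / average N | Immediate outcomes |
|---|---|---|
| 0.20 | 13.7% / 18.2 | 13.5% / 18.2 |
| 0.25 | 25.6% / 16.8 | 25.3% / 16.8 |
| 0.30 | 41.2% / 15.0 | 40.5% / 15.1 |
| 0.35 | 57.6% / 13.2 | 57.0% / 13.2 |
| 0.40 | 73.7% / 10.9 | 72.2% / 11.2 |
| 0.45 | 84.7% / 9.3 | 84.1% / 9.3 |
| 0.50 | 92.2% / 7.6 | 92.1% / 7.7 |

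The largest gaps are 1.5 points and 0.3 patients, both at 0.40. With the printed cells only, average N is 11.8 at 0.40 and 8.3 at 0.50. Those are the like-for-like baselines for step 4.

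**3. Accrual.** 12 x 2/3 = 8 a year, or one patient every 12/8 = 1.5 months. Twenty patients over the planned 3 years is 6.67 a year, one every 1.8 months.

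**4. Delayed onset.** Simulation with entry every 1.5 months, N = patients enrolled, printed cells and no accrual hold. Onset is uniform over the range shown. These ranges are assumptions; the documents give no onset distribution.

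| Onset after SBRT | Average enrolled, true rate 40% | Average enrolled, true rate 50% |
|---|---|---|
| Printed table | 10.9 | 7.6 |
| Immediate, printed cells | 11.8 | 8.3 |
| Within 1 month | 11.7 | 8.4 |
| 1-3 months | 13.2 | 9.7 |
| 0-12 months | 17.1 | 14.6 |
| 3-12 months | 18.3 | 16.4 |

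Onset within 1 month falls before the next entry at 1.5 months, so that row equals the immediate one up to simulation error. Against the immediate baseline, 1-3 month onset adds 13.2 - 11.8 = 1.4 patients at 40%, and 3-12 month onset adds 18.3 - 11.8 = 6.5.

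**5. Probabilities for 3-12 month onset.** Two quantities must be kept apart.
- Ever crossing the boundary (the printed quantity): about 60% at a true 40% and 87% at 50%, against 73.7% and 92.2% printed.
- Crossing while enrolment can still be suspended, before the 20th entry: about 27-30% and 55%, against about 70% and 91% with immediate outcomes.

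**6. Sensitivity, true rate 40%.** With random (Poisson) arrivals and 2 of 2 included, average enrolment at 8 a year (6.67 a year in brackets) is 11.2 (11.2) for immediate outcomes, 11.8 (11.7) for onset within 1 month, 13.4 (13.1) for 1-3 months, 14.6 (14.0) for 0-6 months and 17.9 (17.2) for 3-12 months. A 6-month pause after the six stage 1 patients, which the plan does not state, changes 17.9 only to 17.1.

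**The case against.** The strongest reply concerns size. The documents give no timing for fracture, and myelitis and necrosis appear only as endpoints in the dose-constraint tables. Section 7.1 adds that study doses are below those thought to carry high fracture risk. The toxicities it lists as common, such as skin reactions, nausea and pain, are given no late onset. The one figure for onset within follow-up, 1-3 months, is for an event expected to be uncommon here, and it costs only one or two patients. This stands. A reader might infer that an unsafe rate would usually be flagged only once most or all patients had been treated. That follows from an assumed late onset, not from the documents.

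A reader might also set 55% or 28% suspension against the printed 92.2% or 73.7%. Those are different quantities: the first is suspension before the 20th entry, the second is declaring the treatment unsafe at any point. On the printed quantity the fall for 3-12 month onset is to about 87% and 60%. A late crossing still flags the treatment, although no enrolment is then left to suspend.

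Other safeguards exist. A possibly related Grade 5 event suspends accrual by itself, the Safety Monitoring Committee follows the trial, and toxicity is tabulated with exact intervals. They limit the consequence, but none defines N or a window, and the Grade 5 rule does not cover Grade 3-4 events.

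**Conclusion.** The point holds as a conditional one. The printed operating characteristics are those of an immediate-outcome calculation, and nothing in the plan makes outcomes immediate or deals with pending patients. Taking N as patients treated, which sections 9.1.1 and 13.4.1 point to, the rule suspends later than stated whenever toxicity tends to appear after further patients have entered.

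The mechanism is certain; the size is not. At a true rate of 40%, the delay is negligible to under one patient for onset within 1 month, about 1.4 to 2.2 patients for 1-3 months (13.2 - 11.8 with fixed entry, 13.4 - 11.2 with random arrivals), and about 6.5 patients for 3-12 months. The documents do not say which applies. They do name late effects and assess toxicity to 36 months, so immediate onset cannot simply be presumed. The table should be corrected, but it does not follow that the trial lacks safety oversight.

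**What to change.** In section 11.2:
1. State the toxicity window to which the rule applies. Its length is for the sponsor to choose.
2. Define N by that window, for example AE cases plus the fraction of the window completed by each AE-free patient, or only patients with an AE or a completed window.
3. Re-simulate at the planned accrual over a range of onset times. Report both the probability of ever crossing and the probability of crossing before the last entry.
4. If N is redefined, recheck the boundary and recalibrate it if needed so that suspension at a true 20% stays near the 13.7% already accepted.
5. Replace the printed table, and say whether 2 of 2 suspends.

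Step 4 is needed because AEs would enter N at once while AE-free patients enter slowly, which pushes the observed rate up. With the boundary unchanged and a 12-month window taken for illustration, crossing at a true 20% is about 7-20% for follow-up-weighted N and 20-40% for completed-window N, depending on onset and rounding. Redefining N while keeping the boundary is therefore not safely within the accepted 13.7%.

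The cost is wording and one re-simulation, a less favourable average sample size in print, and possibly a revised boundary. No visits or patients are added.

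### Section 11.2: the boundary table has no stop at 2 AEs in 2 patients, although the stated 65% criterion implies one and the printed operating characteristics appear to include it

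*Combined protocol and SAP*

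**What the plan says.** Everything relevant is in Section 11.2 (Stopping Rules) of the combined protocol and SAP.

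- **Monitoring:** "The study will enroll 20 patients and toxicity will be monitored continuously throughout". No minimum number of patients before the rule applies is given.
- **Prior:** "The prior distribution for the risk of AE is beta (0.5, 3.5), representing our prior guess at the AE rate is 12.5% on average".
- **Criterion:** "if the posterior probability of the AE rate exceeding 30% is 65% or greater, we will consider stopping the study for safety consultation".
- **Boundary table:** the AE counts are "Suspend enrollment if 3 AEs 4 AEs 5 AEs 6 AEs 7 AEs 8 AEs" and the matching patient ranges are "Out of N 3-5 6-8 9-11 12-14 15-17 18-20". The earliest possible suspension is therefore 3 AEs in 3 patients.
- **Operating characteristics:** "The stopping rules and corresponding operating characteristics based on 5000 simulations are shown in the tables below". The second table gives the probability of declaring the treatment unsafe and the average sample size for true AE risks from 0.20 to 0.50.

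**The concern.** The prior, the criterion and continuous monitoring together fix the boundary at every sample size. The printed table should therefore follow from them, and the operating characteristics should follow from the table. After 2 AEs in 2 patients the text calls for a stop to be considered, but the table does not suspend enrollment. A site working from the table would not raise the consultation that the text asks for.

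The operating characteristics are also presented as those of the printed rule. If they belong to a slightly different rule, the protection described to the IRB and the Safety Monitoring Committee is not exactly what the table delivers.

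**Working it through.** **Inputs (all from Section 11.2).** Prior Beta(0.5, 3.5); stop if P(AE rate > 0.30) ≥ 0.65; check after every patient up to 20; 5000 simulations; both printed tables.

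**Step 1: reproduce the boundary.** After x AEs in n patients the posterior is Beta(0.5 + x, 3.5 + n − x). The boundary is the smallest x with P(rate > 0.30) ≥ 0.65.

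| Patients | Highest count that does not stop (smallest n in the range) | Boundary count (largest n in the range) | Criterion | Printed table |
|---|---|---|---|---|
| 1 | 1/1: 0.447 | none | no stop | no stop |
| **2** | – | **2/2: 0.703** | **2 AEs** | **no stop** |
| 3–5 | 2/3: 0.593 | 3/5: 0.692 | 3 | 3 |
| 6–8 | 3/6: 0.604 | 4/8: 0.689 | 4 | 4 |
| 9–11 | 4/9: 0.614 | 5/11: 0.690 | 5 | 5 |
| 12–14 | 5/12: 0.624 | 6/14: 0.692 | 6 | 6 |
| 15–17 | 6/15: 0.633 | 7/17: 0.696 | 7 | 7 |
| 18–20 | 7/18: 0.641 | 8/20: 0.699 | 8 | 8 |

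For 2 of 2 the posterior is Beta(2.5, 3.5). All other cells agree.

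**Step 2: could another threshold explain the gap?** To give the printed boundaries for 3 to 20 patients, the threshold must lie above 0.641 (7 of 18 must not stop) and at or below 0.689 (4 of 8 must stop). Since 2 of 2 gives 0.703, any threshold in that range also stops there. Only an unstated three-patient minimum would produce the printed table.

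**Step 3: exact operating characteristics.** These were obtained by forward recursion over the AE count, stopping as soon as the boundary is reached, up to 20 patients. Each cell shows stopping probability / mean N.

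| True risk | Stated | Exact, printed table | Exact, 2 of 2 added |
|---|---|---|---|
| 0.20 | 13.7% / 18.2 | 11.8% / 18.6 | 13.5% / 18.2 |
| 0.25 | 25.6% / 16.8 | 23.5% / 17.3 | 25.3% / 16.8 |
| 0.30 | 41.2% / 15.0 | 38.8% / 15.6 | 40.5% / 15.1 |
| 0.35 | 57.6% / 13.2 | 55.7% / 13.7 | 57.0% / 13.2 |
| 0.40 | 73.7% / 10.9 | 71.3% / 11.8 | 72.2% / 11.2 |
| 0.45 | 84.7% / 9.3 | 83.6% / 9.9 | 84.1% / 9.3 |
| 0.50 | 92.2% / 7.6 | 91.8% / 8.3 | 92.1% / 7.7 |

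**Step 4: is the difference simulation noise?** z = (stated − exact) / (SD/√5000). For example, at risk 0.20 under the printed table, the SD of N is 4.20, so the SE is 4.20/√5000 = 0.059 and z = (18.2 − 18.57)/0.059 ≈ −6.2.

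- *Printed table:* stated mean N is too low in all seven rows, by 5.6 to 9.3 SE (5.1 to 8.7 after allowing 0.05 for rounding). Stated stopping probabilities are too high in all seven rows. The sum of squared z-scores for the probabilities is 68.9 on 7 df, p ≈ 2 × 10⁻¹².
- *2 of 2 added:* mean N is within about 1.1 SE in six rows. The sum of squares is 9.4 on 7 df, p = 0.22. The 0.40 row is 2.4 SE off in probability and 2.7 SE off in mean N (about 2.2 after the rounding allowance).

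**Step 5: practical size.** Adding 2 of 2 raises the stopping probability by 0.3 points (risk 0.50) to 1.8 points (risk 0.25), and lowers mean N by 0.4 to 0.6 patients. The chance that the first two patients both have an AE is p²: 4% at risk 0.20, 9% at 0.30 and 25% at 0.50. The chance that this happens and the printed table has still not suspended by patient 5 is p²(1 − p)³. That is 0.04 × 0.512 = 2.0% at risk 0.20, and it peaks at 0.16 × 0.216 = 3.5% at risk 0.40.

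**The case against.** The strongest reply is that this is one missing cell, not a three-way conflict. The criterion is written out in full, monitoring is continuous, and the operating characteristics fit the criterion, so a team following the text would act at 2 of 2 without the table. That is fair as a description: the boundary table is the odd one out. But the text also presents the tables as the stopping rules, so a site may well work from the table alone.

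Second, the exposure is small. It arises only if both of the first two patients have a qualifying event, and the table then suspends at the next AE in patients 3 to 5. The Grade 5 rule and Safety Monitoring Committee oversight also apply, and the wording is only that stopping will be considered. This stands and limits the weight of the point. The large z-scores and small p-value show that the printed figures belong to a different rule; they do not show a large safety effect.

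Third, the 0.40 row may be noise. The seven rows together are compatible with the rule that includes 2 of 2 (p = 0.22). The largest of seven independent deviations reaches 2.4 SE about 11% of the time (1 − (1 − 0.016)⁷). The two measures come from the same simulated trials and are not separate evidence. This also stands: rechecking that row is a minor request, not a finding of error.

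Finally, a column could have been lost when the PDF was read. Six AE counts pair with six patient ranges, so this is unlikely, though it cannot be fully excluded.

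**Conclusion.** The inconsistency is real. Under the stated prior and criterion, 2 AEs in 2 patients meets the stopping condition (0.703 against 0.65), and the printed table does not stop there. The printed operating characteristics are not those of the printed table, and they fit much better with 2 of 2 included. A silent three-patient minimum would explain the table but not the operating characteristics.

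This is a correctable inconsistency in the safety rule, not a large loss of protection. The conclusion assumes that the rule is checked after each patient's outcome is known, that each patient counts at most once, and that the table is complete as read. It should be corrected, with high confidence in the arithmetic.

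**What to change.** Reconcile Section 11.2 in one of two ways; the choice is the sponsor's.

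1. Add a column for 2 AEs out of 2 to the boundary table, as the stated criterion implies. The stated operating characteristics can then largely stay.
2. State that the rule applies only from the third patient, keep the boundary table, and replace the operating characteristics with the exact values for the printed boundaries given above.

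In either case recheck the 0.40 row. Exact recursion is quick and removes simulation error altogether.

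The cost is one table column, or one sentence and a replaced table. Sample size does not change. Option 1 raises the chance of a safety pause by 0.3 to 1.8 points relative to the printed table, an increase that the stated figures largely already contain.
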